5. *Quality control imaging data* (C2). The pilot data were in 9-12 or 12-18 year-olds, which cover the age range (i.e. 11-13 years) in the proposed study (**IIIC.3**). Our neuroimaging studies have included youth as young as 6 years, with reliable data in 93%-97% of the samples (**IIIC.4f.2b.2**). We implement many reliable data collection methods (**IIIC.4f.2b.1, 2b.2**). We also institute established methods to reduce dropout rates (**IIIC.10a**). So, the estimated 20% dropout rate is easily attainable. Should this not prove to be the case, we agree with the reviewer: "this concern is mitigated by the robust recruitment mechanisms in place which could supply additional subjects."

6. *Motion artifacts* (C2). We propose several methods to address motion artifact at individual level. These metrics can be summarized to a single number and then compared between groups or used as covariates (**IIIC.4f.2b.6**).

7. *Power analysis* (C2). To avoid biased estimates from small sample sizes, we used *minimum detectable effect size* (ES) at a clinically meaningful level. ES from pilot data (.3-.5) are consistent with the power analysis (**IIIC.7e**).

8. *fMRI tasks not novel* (C3). We deliberately selected theoretically-based, well-established tasks in this novel study on neural basis of a prevention program. Untested tasks could lead to confounds in interpreting the results.

9. *Miscellaneous*. IQ should be  $\geq 80$  (C3). We will provide laptops to those who don't own them (C3; **IIIC.4f.6**).

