Method 1: *Youth will be randomized to a 6-week PAAS intervention or a wait-list condition. Functional magnetic resonance imaging (fMRI) scans will be acquired at rest and in response to a task involving the balance between reward-drive and cognitive-control circuits pre- and post-intervention to assess functional connectivity changes.*

Hypothesis 1: PAAS will produce a greater balance in reward-drive and cognitive-control systems (by increasing functional connectivity between these two components of the neural circuitry) compared to the wait-list condition.

**Specific Aim 2:** Evaluate if the post-intervention neural changes mediate PAAS' effects on youth self-regulation.

Method 2: *Direct and indirect (i.e. functional connectivity) effects of PAAS on youth cognitive and emotional self-regulation measured three months post-intervention will be assessed to identify which neural changes mediate PAAS' effects on these self-regulation measures.*

Hypothesis 2: PAAS-induced changes in self-regulation will be mediated by PAAS' effects on the neural circuitry.

**Exploratory Analyses:** We will identify subgroups of youth who benefit more from PAAS intervention effects on self-regulation defined by demographic, neurobiological and social-contextual factors (e.g. individual differences in baseline functional connectivity may predict who benefits most from the intervention [IIIC.3c, **Fig 3**]).

The expected outcomes of Aims 1 and 2 will contribute to an integration of our understanding of neural circuitry governing adolescent decision-making and of the effectiveness of an intervention shown to reduce HIV-related risky behaviors among AA youth. These outcomes will positively impact efforts to improve interventions that target high-risk behavior in youth from other ethnic/racial groups by linking biological mechanisms, psychological processes, social-contextual factors and behavioral outcomes associated with these interventions.

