### III C. APPROACH

**IIIC.1 Overview:** The conceptual model guiding our study is presented in **Fig 1**. Aim 1 will assess the effects of PAAS on the magnitude of Phase 2 functional connectivity between reward-drive and cognitive-control neural circuitry at rest and during a decision-making task after controlling for pre-intervention (Phase 1) levels. Aim 2 will evaluate if Phase 2 post-treatment neural circuitry changes mediate PAAS' effects on psychological processes (i.e. cognitive and emotional self-regulation) at the 3-month follow-up (Phase 3) after controlling for Phase 1 values. Our overarching hypothesis is that the functional connectivity between reward and cognitive-control networks correlates with self-regulation, and that PAAS increases the magnitude of functional connectivity between these neural networks. In addition to these hypotheses, we will identify characteristics (demographic, neurobiological, psychological, behavioral and social-contextual factors) that moderate PAAS' effects on the relationship between functional brain changes and cognitive-emotional self-regulation in exploratory analyses (IIIC.3b; **Fig 2**).

A total of 128 AA volunteers (ages 11-13 years, 50% male and female) and 128 parents (primary caretakers) will be recruited. Youth and parents will complete assessments on intervention targets (i.e. parenting processes, youth psychological protective factors and cognitions/behaviors associated with HIV and SUD vulnerability). fMRI scans will be acquired in the youth to assess functional connectivity between reward-drive and cognitive-control neural circuitry during rest and while performing a decision-making task involving probabilistic monetary rewards. A second task that assesses general impulsivity/motor response inhibition (in contrast to reward-drive) will be included as a supplementary measure. Following assessments, the families will be randomized to either PAAS or a wait-list control condition for 6 weeks. fMRI scans will be repeated after 6 weeks to measure functional brain changes from pre-to-post intervention. They will repeat the intervention-targeted assessments 3 months later, after which the wait-list controls will be offered PAAS as a benefit for participation in the study (IIIC.4f.1; **Fig 6**).

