### IIIC.7. Statistical Methods

**IIIC.7a. Data Management:** Data management will be done via remote electronic data capture (*REDCap*). REDCAP was developed at VUMC to insure data integrity and completeness, including compliance with HIPAA (over 300,000 users). Data will be entered immediately after testing on data entry screens designed to duplicate the data collection forms (ACASI; **IIIC.4f.4**). Reports can be generated to track all contacts with the participants.

**IIIC.7b. Procedures for Handling Missing Data:** Missing data will be accounted for by including "missingness" as a covariate if the proportion of missing data is small, or alternatively using multiple imputation methods if the proportion of missing data is large, e.g. >5%.

**IIIC.7c. Data Reduction:** Each hypothesis will be examined using a primary variable, with supplemental information gained from analysis of other related measures (**see IIIC.5**).

**IIIC.7d. Data Analysis:** Descriptive statistics (e.g. means and standard deviations, frequencies and histograms) will be computed for all variables, along with 95% bootstrap confidence intervals. Significance tests will be two-tailed, with  $p < 0.05$ , controlling for multiple comparisons. Pubertal stage/gonadal hormones, gender and SES will be included as concomitant variables in analyses where they are known to correlate with the outcome. These covariates, while not of primary interest, will reduce residual variance and increase the precision of effect estimates for improved statistical power. Secondary analyses will determine if these covariates significantly affect the outcomes. Behavioral/emotional problem score (CBCL/YSR), lifetime history of substance use and dose of the intervention (number of completed sessions) will serve as additional potential covariates.

**IIIC.7d.1. Hypothesis 1:** PAAS will induce greater functional connectivity changes in the reward-drive and cognitive-control (fronto-striatal) circuitry compared to the wait-list condition. Post-treatment neural connectivity

scores will be regressed on group assignment (PAAS vs. wait-list) as the independent variable and baseline (pre-treatment) neural connectivity score as a covariate. Two separate models will be run for resting-state and task-based fMRI connectivity measures. Other covariates (IIIC.7d) will be included if there are group differences.

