**IIIC.7d.2. Hypothesis 2: PAAS-induced changes in youth self-regulation (cognitive and emotional regulation) at 3 months will be mediated by PAAS' effects on changes in neural circuitry.** A mediation process will be modeled using a sequential process of the associations between specified brain responses and self-regulation. The Wager/Lindquist Mediation Toolbox (IIIC.4f.2b.6) will be deployed. Mediation effects are estimated from the product of the regression coefficient (a) when a mediator of interest (e.g. neural response) is regressed on the intervention and regression coefficient (b) when the outcome criterion (self-regulation at 3 mon.) is regressed on the mediator, controlling for the intervention effect. The standard error of the mediated effect can be calculated in various ways, including the bootstrap method. This method is referred to as the product-of-coefficients approach for testing mediation, and provides an efficient overall test of mediation processes.

**IIIC.7d.3. Exploratory Analyses:** We will examine whether baseline characteristics moderate PAAS' effect (e.g. if reward-drive [BAS] score/ neural connectivity in the fronto-striatal circuit interacts with PAAS) on improvement in self-regulation. We will assess the association of neural changes (local/whole brain) with behavioral and social-contextual variables targeted by PAAS (i.e. risky behaviors and parenting behavior). Other functional connectivity changes (e.g. default-mode, cognitive and salience networks, and the fronto-limbic circuit) will be identified and the association between functional connectivity patterns at rest and during task performance will be evaluated.

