**Table 3. Timeline of Research Activities**

Research Activities Per Quarter	Year 01				Year 02				Year 03				Year 04				Year 05			
	1	2	3	4	1	2	3	4	1	2	3	4	1	2	3	4	1	2	3	4
Train staff, set up database	x	x																		
Recruit subjects and conduct baseline assessments		x	x	x	x	x	x	x	x	x	x	x	x	x	x	x	x	x	x	x
Implement PAAS intervention for the active group		x	x	x	x	x	x	x	x	x	x	x	x	x	x	x	x	x	x	x
Post-intervention measures			x	x	x	x	x	x	x	x	x	x	x	x	x	x	x	x	x	x
Follow-up assessments (3 months post-treatment)				x	x	x	x	x	x	x	x	x	x	x	x	x	x	x	x	x
Implement PAAS for the wait-list group				x	x	x	x	x	x	x	x	x	x	x	x	x	x	x	x	x
Data entry and management	x	x	x	x	x	x	x	x	x	x	x	x	x	x	x	x	x	x	x	x
Data analysis																x	x	x		
Preparation of manuscripts																x	x	x		

**IIIC.9. Expected Outcomes and Future Directions:** The study is expected to contribute new knowledge in the following areas: (1) whether functional connectivity changes in decision-making (a balance between reward-drive and cognitive-control) neural circuitry occur in response to a preventive intervention (PAAS); (2) whether these functional connectivity changes mediate the improvement in youth self-regulation processes that are targeted by the intervention; (3) whether socio-demographic features, reward-drive traits and baseline functional connectivity can identify subgroups of youth who respond better to the intervention; and (4) if intervention-induced changes in functional connectivity and self-regulation are associated with a reduction in risky behaviors (willingness and intentions). The study will advance the benefits of PAAS and other evidence-based programs by improving our understanding of the ways in which neurobiological mechanisms affect intervention-induced behavioral changes.

If, indeed, brain changes in the decision-making circuitry mediate the intervention effects on self-regulation and risky behaviors, the intervention program can be tailored to individual youth to improve outcomes. Novel pharmacological, psychosocial and neurofeedback treatments can be developed *to target specific neural circuits* as adjunctive interventions for reducing risky behaviors in this population. Additionally, “personalized”

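### IIIC.7d.2 writes the Hypothesis 2 mediation paths without a Phase 1 term and leaves the mediator undefined, while IIIC.1 promises control for Phase 1 values; the two sections must be reconciled

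*Combined protocol and SAP*

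**What the plan says.** Three places bear on the Aim 2 model.

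- **IIIC.1 (Overview)** says mediation of the effect on self-regulation is evaluated "at the 3-month follow-up (Phase 3) after controlling for Phase 1 values". It does not say whether this means connectivity, self-regulation or both, or which path the terms enter.
- **IIIC.7d.2 (Hypothesis 2)** sets out the product-of-coefficients method. Path a is the model in which "a mediator of interest (e.g. neural response) is regressed on the intervention". In path b the 3-month outcome "is regressed on the mediator, controlling for the intervention effect". Neither names a Phase 1 variable.
- **IIIC.7d.1 (Hypothesis 1)**, directly before it, does name its adjustment: "baseline (pre-treatment) neural connectivity score as a covariate".

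The general covariates in IIIC.7d are pubertal stage or hormones, gender, SES, CBCL/YSR score, substance-use history and number of sessions. Baseline connectivity and baseline self-regulation are not among them. IIIC.7e refers to a repeated measures model with covariates but does not specify it.

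The mediator is also not fixed. Specific Aim 2 reads "Evaluate if the post-intervention neural changes mediate PAAS' effects on youth self-regulation", the Hypothesis 2 statement says the effect "will be mediated by PAAS' effects on changes in neural circuitry", and IIIC.9 asks "whether these functional connectivity changes mediate the improvement in youth self-regulation processes". The path a sentence instead offers a neural response as its example.

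**The concern.** Randomisation protects path a, the effect of PAAS on connectivity. It does not protect path b, because nobody is randomised to a level of connectivity. If youth with stronger fronto-striatal connectivity at Phase 1 also have better self-regulation at Phase 1, and both measures persist, then Phase 2 connectivity and 3-month self-regulation are associated even when connectivity does nothing. Such a correlation is the trial's own working hypothesis (IIIC.1), and the resting-state pilot in 25 children (numbered IIC.3e) reports correlations between risk-related traits and striatal connectivity.

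The text allows at least three readings: an unadjusted post-treatment level, an unadjusted change score, and a baseline-adjusted model. They can give different Aim 2 conclusions from the same data. Aim 2 is one of the two specific aims, and IIIC.9 builds tailoring of the programme on it.

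**Working it through.** **Plan's own figures.** IIIC.6 and IIIC.7e: 128 × 0.8 = 102.4, so N = 102, or 51 per arm. The stated detectable r = .31 (R² = .10) is reproduced by the omnibus R² test with three predictors, which gives power 0.799. The number of predictors is not stated; one predictor gives 0.915 and four give 0.753. These figures are not disputed.

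**Inputs not in the documents (assumed).** These are the baseline correlation r, the stability of each measure (sM for connectivity, sY for self-regulation) and the PAAS shift in connectivity. The resubmission introduction says "ES from pilot data (.3-.5) are consistent with the power analysis" but gives no metric. If r = .31 is read as the group effect, the shift is d = 2r/√(1 − r²) = 0.62/√0.9039 = 0.65 SD.

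**Bias in path b, autoregressive model, unit variances, no Phase 1 term.**

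- Post-treatment level as mediator: expected b = true b + sM·sY·r.
- Unadjusted change score as mediator: expected b = (true b)/2 − sY·r/2.

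With sM = .5, sY = .6, r = .3:

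- True b = 0: level .5 × .6 × .3 = +.09; change −.6 × .3/2 = −.09. Simulated means at N = 102 are .090 and −.091.
- True b = .3: level .3 + .09 = .39 (simulated .389); change .15 − .09 = .06 (simulated .059).
- Adjusted for both baselines: simulated b is .001 and .298. The two mediator definitions then coincide, because subtracting a covariate already in the model does not alter the other coefficients.
- Adjusted for one baseline only, true b = 0: mean b is zero to two decimals with either Phase 1 measure alone.

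The sign follows r. At r = −.3 and stability .5 the level formula gives .5 × .5 × (−.3) = −.075 (simulated about −.07).

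**False mediation.** True b = 0, 51 per arm, a and b both significant at two-sided .05 in either direction, equal stability of .5 to .7, autoregressive model:

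| PAAS shift | Unadjusted level, r = .1 | r = .2 | r = .3 | Both baselines |
|---|---|---|---|---|
| 0.3 SD | 2.0%-2.6% | 2.7%-5.0% | 3.4%-9.7% | 1.8%-2.9% |
| 0.5 SD | 4.0%-5.3% | 5.4%-11.4% | 8.2%-21.6% | 4.0%-4.9% |
| 0.65 SD | 5.4%-6.8% | 7.0%-14.7% | 10.3%-27.6% | 4.5%-5.3% |

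With no shift the unadjusted rate is at most 1.8%, because path a is then rarely significant. At 0.65 SD and r = .2 to .3, the unadjusted change score gives mean b of −.05 to −.11 and false support for Hypothesis 2 in under 1%.

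A percentile bootstrap agrees with the joint test at 0.65 SD. The unadjusted level gives 8.4% (r = .2, stability .5) and 30.0% (r = .3, stability .7), against 5.0% and 4.8% with both baselines.

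**A different persistence model.** Suppose each measure is a stable trait plus independent noise. The unadjusted level bias is then the full observed r, whatever the stability, and the change score is unbiased at true b = 0. At 0.65 SD and r = .2 to .3, false mediation is 47%-79% unadjusted, 7%-19% with both baselines and 4%-5% with an unadjusted change score. Observed r of .2 to .3 with repeat correlations of .5 to .7 implies trait correlations from .2/.7 = .29 to .3/.5 = .60.

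**Power.** With true b = .3, r = 0 and a shift of 0.5 to 0.65 SD, across both persistence models: both baselines 68%-83%, unadjusted level 58%-76%, unadjusted change score 18%-28%.

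**The case against.** The strongest reply is that the plan already commits to the adjustment. IIIC.1 promises control for Phase 1 values, and IIIC.7d.1 turns neural change into a post-treatment score with baseline as covariate. Read together, the natural Aim 2 model is the one recommended here. IIIC.7d.2 also reads like a textbook account: it names no seed region, task or scale, and it leaves the standard-error method open. The general covariates are missing from its equations too, although IIIC.7d applies them across analyses. Silence there is weak evidence of exclusion.

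Much of this stands. A reader might infer that the sponsor has chosen to test mediation without baseline adjustment, and the documents do not support that. The harm also needs several things together: the IIIC.1 commitment is not carried out, PAAS shifts connectivity, and the two measures are correlated at baseline and persist. With a small shift and a low correlation, nothing material happens.

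The reply does not supply the missing model. IIIC.1 does not say which Phase 1 variables enter which path, no other section does, and the mediator wording varies within IIIC.7d.2 itself. An analyst could defend any of the three readings from the text.

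**Conclusion.** The point holds as a conflict and under-specification between IIIC.1 and IIIC.7d.2. It should be settled before the Aim 2 analysis.

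If the IIIC.7d.2 equations were run literally, the direction of the bias would depend on the reading. A post-treatment level mediator is biased towards Hypothesis 2 when the baseline correlation is positive. An unadjusted change score is biased the opposite way in an autoregressive model. A reader might infer that the bias always favours PAAS; it does not, and the pilot correlations in IIC.3e differ in sign by region.

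The size cannot be derived from the documents. Under the autoregressive assumptions it runs from nothing material (5% or less at a 0.3 SD shift with r of .2 or less; at most about 2% with no shift) to about 7%-28% at 0.65 SD with r of .2 to .3, against about 5% adjusted. A reader might take 47%-79% as the headline. That range belongs to the trait-plus-noise model with trait correlations of about .29 to .60, for which the documents give no support. Confidence is high on the textual conflict and moderate on its practical importance.

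**What to change.** Write the Hypothesis 2 models out in IIIC.7d.2 so that they carry out IIIC.1:

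- **Path a:** post-treatment connectivity on group and Phase 1 connectivity.
- **Path b:** 3-month self-regulation on post-treatment connectivity, group, Phase 1 connectivity and Phase 1 self-regulation.
- Bootstrap the product a·b from these two models, and enter the same covariates in the mediation toolbox.

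With Phase 1 connectivity in both paths, level and change mediators give the same a and b, so the wording conflict no longer matters.

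Add two sentences of limitation. Path b remains observational. If both measures behave as a stable trait plus noise, the two-baseline model reduces false mediation but does not remove it. Either baseline alone is enough in the autoregressive case; both are recommended because the persistence model is unknown and the pair gave better power than no adjustment.

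A change-score mediator may be reported as an optional sensitivity analysis. It is a poor primary choice because its power for a true effect was much lower.

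The cost is wording plus one or two degrees of freedom. IIIC.4f.1 already schedules the Phase 1 scans and psychosocial measures, and repeats the latter at Phase 3.

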**Table 3. Timeline of Research Activities**

Research Activities Per Quarter	Year 01				Year 02				Year 03				Year 04				Year 05			
	1	2	3	4	1	2	3	4	1	2	3	4	1	2	3	4	1	2	3	4
Train staff, set up database	x	x																		
Recruit subjects and conduct baseline assessments		x	x	x	x	x	x	x	x	x	x	x	x	x	x	x	x	x	x	x
Implement PAAS intervention for the active group		x	x	x	x	x	x	x	x	x	x	x	x	x	x	x	x	x	x	x
Post-intervention measures			x	x	x	x	x	x	x	x	x	x	x	x	x	x	x	x	x	x
Follow-up assessments (3 months post-treatment)				x	x	x	x	x	x	x	x	x	x	x	x	x	x	x	x	x
Implement PAAS for the wait-list group				x	x	x	x	x	x	x	x	x	x	x	x	x	x	x	x	x
Data entry and management	x	x	x	x	x	x	x	x	x	x	x	x	x	x	x	x	x	x	x	x
Data analysis																x	x	x		
Preparation of manuscripts																x	x	x		

**IIIC.9. Expected Outcomes and Future Directions:** The study is expected to contribute new knowledge in the following areas: (1) whether functional connectivity changes in decision-making (a balance between reward-drive and cognitive-control) neural circuitry occur in response to a preventive intervention (PAAS); (2) whether these functional connectivity changes mediate the improvement in youth self-regulation processes that are targeted by the intervention; (3) whether socio-demographic features, reward-drive traits and baseline functional connectivity can identify subgroups of youth who respond better to the intervention; and (4) if intervention-induced changes in functional connectivity and self-regulation are associated with a reduction in risky behaviors (willingness and intentions). The study will advance the benefits of PAAS and other evidence-based programs by improving our understanding of the ways in which neurobiological mechanisms affect intervention-induced behavioral changes.

If, indeed, brain changes in the decision-making circuitry mediate the intervention effects on self-regulation and risky behaviors, the intervention program can be tailored to individual youth to improve outcomes. Novel pharmacological, psychosocial and neurofeedback treatments can be developed *to target specific neural circuits* as adjunctive interventions for reducing risky behaviors in this population. Additionally, “personalized”

interventions can be developed for specific subgroups of at-risk youth to reduce risky behaviors and their long-term consequences. These methods may include, for example, the development of biopsychosocial profiles that can be used efficiently to focus intervention efforts. Recent studies in animals and humans have suggested that behavioral and psychological manipulations, including diet, exercise and CBT can induce neural changes. The neural markers can be used to predict treatment outcome more effectively and to index treatment response in RCTs, which then can change clinical practice and public policy.

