#### IIIC.4f. Methods

**IIIC.4f.1. Overview:** A description of the protocol/procedures is provided (IIIC.4f.2 - IIIC.4f.6; **Fig 6, Table 1**). Eleven-to-thirteen year-old AA youth and their parents will complete information on demographic and health status as part of their clinic visits. Families selected randomly from the eligible pool will be invited to participate, while at the clinic or later via mail (**IV.A.2a, Human Subjects**). Research is an integral part of these participating clinical programs and processes are in place for a smooth transition from clinical care to research that follows the Institutional Review Board and Health Insurance Portability and Accountability Act (HIPAA) guidelines. When contact is made, they will be provided information about the study, with an overview of the time commitment and assessments. Interested families will be screened further to determine eligibility by obtaining medical, psychiatric and treatment history.

**Phase 1 (Pre-intervention Assessments):** Information on psychiatric symptoms, psychosocial factors and risky behaviors will be completed. Those who meet eligibility criteria will have a blood draw for gonadal hormones and receive training on the fMRI tasks and have a mock scan. A urine sample will be obtained to test for alcohol/drug use and pregnancy. They then will complete baseline fMRI studies. **Phase 2 (Intervention Phase):** The families will be randomized using procedures described in IIIC.4f.5 to PAAS or wait-list condition (1:1 ratio) for the 6-week intervention period. PAAS consists of 6 web- or DVD-based weekly sessions, 90 minutes per session; the first half includes individual, concurrent curricula for caregivers and youth, and the second half is a family-joint session designed for practicing the skills learned in the individual sessions. At the end of the 6-week intervention period, the urine drug test and fMRI studies will be repeated in both groups. **Phase 3 (Follow-up Phase):** Three months after the intervention phase, both psychosocial and risky-behavior assessments will be repeated. The wait-list group then will be offered the PAAS intervention as a benefit for participation in the study.

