				5-10 Days		Starts within 14 Days of Screen						
				1	2	3	4	5	6	7	8	
Visit	Parent	Youth	Minutes			Wk 1	Wk 2	Wk 3	Wk 4	Wk 5	Wk 6	
Intervention Week												
Clinic/Telephone Screen	X	X	15-30	X								
Informed Consent/Assent	X	X	45-60			X						
Demographic Information	X		10-20			X						
Psychiatric Diagnostic Screen	X	X	30-60			X						
Youth Beh/Emotional Problems	X	X	20-30			X						
Reward-drive Traits		X	15-20			X						
Risky Behaviors		X	15-20			X						
Resistance Efficacy		X	10-15			X						
Self-control		X	15-20			X						
Future Orientation		X	10-15			X						
Emotion Regulation		X	5-10			X						
Self-image		X	5-10			X						
Self-esteem		X	5-10			X						
Impulsivity		X	5-10			X						
Involved-vigilant Parenting	X	X	10-15			X						
Risk-behavior Communication	X	X	10-15			X						
Adaptive Racial Socialization	X	X	10-15			X						
MRI Safety Screen	X	X	5-10			X						
Handedness Scale		X	5-10			X						
Tanner Stages		X	5-10			X						
Serum Gonadal Steroids		X	10-15			X						
Urine Alcohol/Drug Test		X	10-15			X						
Urine Pregnancy Test		X	0			X						
Task Practice/Mock Scanner		X	60-90			X						
Resting and Task-based fMRI		X	90-120			X						
PAAS Intervention	X	X	90-100			X	X	X	X	X	X	

and most of the cerebellum (TR/TE = 2000/25 msec, FOV = 24 cm, matrix = 64 × 64). This sequence was designed to preserve the signal in the striatum and ventral PFC, areas which are susceptible to signal drop-out. An automated higher-order shim procedure will be applied to minimize potential magnetic field inhomogeneities.

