5	Protecting against dangerous behavior	Understand risk prevalence, overall and for your community; Importance of being an approachable parent	Peer pressure; parents' concerns about peer affiliation	Identify peer pressure; compare risk engagers from non-risk engagers; dealing with temptation; prosocial peer affiliation	Caregivers and youth working together to protect youth from risk behaviors	Develop family plan for handling peer pressure and temptation; share expectations and values about risk and friendship
6	Parental protections that reduce high risk behaviors	Learn how to effectively monitor youth; understand the prevalence of sexual activity in teens; establish expectations about sex	Dealing with sexual and substance use temptations	Identifying and avoiding dangerous situations; connecting temptations, dreams, goals, school and future orientation	Our family plan and pledge for positive youth development	Share expectations, dreams, and hopes; discuss/identify family strengths; establish a family creed of strength, growth and competence

**IIIC.5. Primary Outcome Criteria:** Primary outcome variables include fronto-striatal functional connectivity at rest and while performing the WOF task and youth psychological protective factors (cognitive and emotional self-regulation). Other neural measures/circuits, psychological/social-contextual and behavioral variables (**Appendix 1**) will be used either as supplementary measures or as potential covariates. By sharpening our focus to *a priori* specified neural circuits and psychological measures, we hope to increase statistical power and, in turn, our ability to identify important differences in the responses of these circuits according to youth protective factors.

**IIIC.6. Sample Attrition:** The team has experience with intensive longitudinal studies involving difficult-to-reach samples with retention rates exceeding 90% for short-term follow-up (**IIIC.10a**). Even with a liberal estimate of 20% attrition, we will have 102 participants, which will give us sufficient power to detect medium effects (**IIIC.7e**).

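### Table 3 closes its only data-analysis window two quarters before recruitment and 3-month follow-up end, so the schedule does not secure the 102 analysable youth behind the power statement

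*Combined protocol and SAP*

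**What the plan says.** Table 3 has 20 quarterly columns. As printed, the relevant rows read:

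- "Recruit subjects and conduct baseline assessments": Year 1 quarter 2 to Year 5 quarter 4 (columns 2-20, 19 quarters).
- "Follow-up assessments (3 months post-treatment": Year 1 quarter 4 to Year 5 quarter 4 (columns 4-20).
- Data analysis, and likewise manuscripts: Year 4 quarter 4 to Year 5 quarter 2 (columns 16-18), then blank.

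Section IIIC.1 sets the sample: "A total of 128 AA volunteers". Section IIIC.4f.1 randomizes families to "PAAS or wait-list condition (1:1 ratio) for the 6-week intervention period", and then: "Three months after the intervention phase, both psychosocial and risky-behavior assessments will be repeated". After that visit the wait-list families are offered the programme.

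Section IIIC.6 states: "Even with a liberal estimate of 20% attrition, we will have 102 participants". Section IIIC.7e rests its power statement (two-sided alpha .05, 80% power, r = .31, R² = .10) on that same 102. Hypothesis 1 (IIIC.7d.1) uses the scan at the end of the 6 weeks. Hypothesis 2 (IIIC.7d.2) uses self-regulation at 3 months. No interim analysis, partial-sample analysis or data-lock rule is described.

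**The concern.** The rows of Table 3 do not fit together. The only analysis period ends at month 54, while enrolment and follow-up are marked to month 60. If the table were followed literally, the primary hypotheses would be tested on whichever youth had finished by then, and the table also enrols youth whose Hypothesis 2 outcome falls after Year 5. Wait-list families enrolled late in Year 5 would likewise have no time within Year 5 to receive the programme they are promised. At stake are the size of the analysed cohort relative to the 102 used for power, and the absence of a rule saying when the confirmatory analysis may be run.

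**Working it through.** **1. The plan's own N.** 128 × (1 − 0.20) = 102.4, so 102 reproduces. In reverse, 102 / 0.80 = 127.5: at 20% attrition, essentially all 128 must have had the chance to complete. At 10% attrition, 102 / 0.90 = 113.3, or 89% of 128.

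**2. Time from enrolment to outcome.** Six weeks (about 1.5 months) plus 3 months is about 4.5 months, or (42 + 91.3) / 91.3 = 1.46 quarters. Table 3's own offset between first recruitment (column 2) and first follow-up (column 4) is 2 quarters. The visit table's window ("Starts within 14 Days of Screen") adds up to about 0.15 quarter, which lies inside this range. For the 6-week scan the lag is 6/13 = 0.46 quarter, or 1 quarter on Table 3's grid.

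**3. Cut-offs that need no accrual assumption.**
- Latest enrolment for a 3-month outcome by the end of the analysis window: 54 − 4.5 = month 49.5.
- Latest enrolment for a 3-month outcome within Year 5: 60 − 4.5 = month 55.5.
- Latest enrolment for a wait-list family to finish the programme within Year 5: 60 − (1.5 + 3 + 1.5) = month 54.

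Recruitment is marked to month 60.

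**4. Expected counts under even accrual (an assumption).** The rate is 128 / 19 = 6.74 per quarter. Youth reaching an assessment by the end of quarter T with lag L number 128 × (T − L − 1) / 19, multiplied by retention. For Hypothesis 2 at T = 18 this gives 128 × (18 − 1.46 − 1) / 19 = 104.7, or 101.1 with L = 2. At T = 20 it gives 118.2 or 114.5.

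| | End of analysis window (month 54) | End of Year 5 (month 60) |
|---|---|---|
| Hypothesis 2, 20% attrition | 81-84 | 92-94 |
| Hypothesis 2, 10% attrition | 91-94 | 103-106 |
| Hypothesis 1, 20% attrition | 86-89 | 97-100 |
| Hypothesis 1, 10% attrition | 97-100 | 109-112 |

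**5. Accrual that would remove the problem.** For all 128 to finish follow-up by month 54, the rate must be 128 / 15.54 = 8.2 to 128 / 15 = 8.5 per quarter. For month 60 it must be 128 / 17.54 = 7.3 to 128 / 17 = 7.5. Either way recruitment ends before the last marked quarter.

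**6. Power.** These are noncentral F calculations with λ = N × R² / (1 − R²) and alpha .05. The protocol's statement is best reproduced by an overall test of three predictors: at N = 102 and R² = .10, power is 79.9%. A 1-df test gives 91.5% there. At N = 84:
- 1-df test: about 84% at r = .31 and 86% at R² = .10.
- Three-predictor test: about 70% at R² = .10.

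These figures are for a regression test. Power for the Hypothesis 2 mediation test was not calculated.

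**The case against.** Table 3 is described as an expected timeline and carries no enrolment numbers. Under IIIC.4f.5 randomization continues only until the matched pairs are filled, so enrolment stops at 128 whenever that happens. Section IIIC.4a regards recruiting 128 as readily achievable, and a rate of 8.2-8.5 per quarter would have everyone through follow-up by month 54. Section IIIC.6 calls 20% attrition liberal and cites "retention rates exceeding 90% for short-term follow-up"; section IIIC.10a reports 10-20% in earlier studies. The response to the previous review also foresees extra recruits if dropout is worse than planned. All of this stands, and it limits the size of the problem.

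A reader might infer that 102 analysable youth cannot exist at the time of analysis, or even by the end of Year 5. The documents do not support that. The first depends on the accrual pattern, which they do not give. The second needs both even accrual and the full 20% attrition; at 10%, 103-106 youth complete.

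A reader might also infer that the stated power is necessarily lost. On a 1-df test it is not: at N = 84, power against the protocol's own r = .31 remains about 84%. Nor do the documents say that between-arm results would be seen during recruitment. The data analysis row could cover image processing or descriptive work.

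Finally, the table was read from PDF by a program, and Table 1 in the same file has visibly lost marks. Every row of Table 3 resolves to 20 cells, and the staggered starts match the visit sequence, so slippage looks unlikely, but the PDF should be checked. None of this explains why the analysis row ends two quarters before the follow-up row.

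**Conclusion.** Provided the printed cell positions are right, the inconsistency is real: the only scheduled analysis ends at month 54, data collection ends at month 60, and late Year 5 enrolees cannot supply the Hypothesis 2 outcome within the study. The direction of the effect at planned attrition follows from 102 being 80% of the full 128. The size rests on even accrual. On that assumption Hypothesis 2 is about 18-21 youth short of 102 when the analysis window closes (8-11 short at 10% attrition), and about 8-10 short at the end of Year 5 only if attrition is the full 20%. Hypothesis 1 is affected less. The power consequence ranges from none against the stated target (1-df test) to a fall from 80% to about 70% at N = 84 (three-predictor test), depending on which regression test the protocol meant. This is a scheduling defect worth correcting, not proof that the trial cannot deliver its sample.

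**What to change.** Check the cell positions against the PDF, then reconcile the rows of Table 3.

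- State a recruitment close early enough for the last youth to complete Phase 3, and for wait-list families to receive the promised programme, within Year 5. For example, closing at the end of Year 5 quarter 1 (month 51) puts the last Phase 3 visit at 51 + 4.5 = month 55.5 and the end of the wait-list programme at month 57.
- Move the confirmatory data analysis to after the last Phase 3 visit and database lock, and state that no between-arm comparison is made earlier.
- If enrolment is to continue as marked, restate the expected analysable N separately for Hypotheses 1 and 2, with the accrual and attrition assumed.

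The cost is a timeline edit and modestly faster accrual: 128 / 16 = 8.0 youth per quarter instead of 128 / 19 = 6.7. In this example the analysis period shortens to 60 − 55.5 = 4.5 months, against the three quarters now marked.
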